6.1.3 Study Period (Day 2 to Day 27)

The study period will be for a duration of 28 consecutive days. The patients will be discharged when the Principal Investigator or a medically qualified Sub Investigator judges that the patient is fit for discharge. All assessments mentioned in [Section 6.3.1.5](#) will be completed before the patient is discharged from the hospital.

The below assessments will be performed as applicable until discharge or Day 28, whichever is earlier.

Study code: NV-05-983-2020
Protocol No.: CVD-04-CD-001
Sponsor name: [name], Limited
Clinical Study Protocol

The clinical status by WHO 10-point ordinal scale and 8-point ordinal scale, NEWS-2 score and COVID-19 associated symptom severity assessment will be evaluated and recorded every day during the study period (until discharge or Day 28, whichever is earlier). Vital signs will be assessed, partial physical examination will be performed every day (until discharge or Day 28, whichever is earlier).

A respiratory tract sample (nasopharyngeal swab or oropharyngeal swab or nasal aspirate or tracheobronchial aspirate or bronchial lavage) will be collected from the patient and sent for detection (qualitative) of SARS-CoV-2 RNA by RT-PCR on Day 5, Day 10 or discharge (if discharge happens earlier than one or more of the above-mentioned assessment timepoints).

Safety assessments [clinical laboratory evaluations (hematology, serum biochemistry, urinalysis)] and 12-lead ECG will be performed on Day 4, Day 7, Day 10, Day 14 and Day 21 or discharge (if discharge happens earlier than one or more of the above-mentioned assessment timepoints). Chest X-ray will be performed on Day 4, Day 7, Day 10 and Day 14 or discharge (if discharge happens earlier than one or more of the above-mentioned assessment timepoints).

Treatment emergent AEs and concomitant medication will be recorded every day.

The status of each individual patient with respect to admission to the Intensive care unit (ICU) of the hospital (with dates of admission and discharge), details of supplemental oxygen received (standard and/or high flow) and details of any mechanical ventilation will be collected every day during the study period (until discharge or Day 28, whichever is earlier).

In case the patient is hospitalized until Day 10, the IMP (Favipiravir/Placebo) will be dispensed for each individual patient in the morning and evening on every study day for 10 days. Patient will take/ be administered the dispensed IMP and treatment compliance will be assessed in the morning and evening on every study day for 10 consecutive days.

If the patient is discharged before Day 10, the required IMP (Favipiravir/Placebo) to complete the remainder of the IMP treatment course will be dispensed to patient at the time of discharge. The patient will be required to continue the remainder of the IMP treatment course at home. The compliance will be evaluated based on details recorded in the patient diary.

End of Treatment (EOT) assessment:

The EOT assessment will be performed on Day 10 (+2 days). A window period of 2 days is applicable only if the patient is discharged before Day 10.

1. If the patient remains in the hospital until Day 10, the EOT will be performed at the site and all the scheduled assessments for Day 10 will be performed (details mentioned in [Section 6.3.1.3](#)).
2. If the patient is discharged before Day 10, the EOT can be performed either as an onsite visit or will be performed at the patient's home.
 - a. On-site visit: If the patient is able to visit the hospital on Day 10, procedures for an unscheduled visit will be performed. Empty blister packs and /or unused IMP will be collected.

Study code: NV-05-983-2020
 Protocol No.: CVD-04-CD-001
 Sponsor name: [name], Limited
 Clinical Study Protocol

OR

- b. At home: If the patient is unable to visit the hospital for the EOT, study nurse or phlebotomist will visit the patient at his/her residence to collect blood sample for safety assessments. A nasopharyngeal swab or oropharyngeal swab will be collected from the patient and sent for detection (qualitative) of SARS-CoV-2 RNA by RT-PCR assay based on Investigator's discretion for individual patients. Empty blister packs and /or unused IMP will be collected. A telephonic follow up will be performed to enquire on treatment emergent AEs experienced, concomitant medication and COVID-19 associated symptom for assessment of clinical relapse.

6.1.4 End of Study-Day 28 (+2 days) or discharge or study discontinuation whichever is earlier

The end of study assessments will be performed on Day 28 or earlier if the patient is discontinued from study or is considered fit for discharge earlier. If the Principal Investigator or a Sub-Investigator judges that the patient is fit for discharge, patient should undergo assessments scheduled for End of Study – Day 28 (+2 days) visit.

The clinical status by WHO 10-point ordinal scale and 8-point ordinal scale, NEWS-2 score and COVID-19 associated symptom severity assessment will be evaluated. Vital signs will be assessed, and partial physical examination will be performed. A respiratory tract sample (nasopharyngeal swab or oropharyngeal swab or nasal aspirate or tracheobronchial aspirate or bronchial lavage) will be collected from the patient and sent for detection (qualitative) of SARS-CoV-2 RNA by RT-PCR assay. Safety assessments [serum pregnancy test for female patients of child-bearing potential, 12-Lead ECG, clinical laboratory evaluations (hematology, serum biochemistry, urinalysis)] will be performed. A chest X-ray will be performed. Treatment emergent AEs and concomitant medication will be recorded.

The status of each individual patient with respect to admission to the Intensive care unit (ICU) of the hospital (with date of discharge, if discharged from ICU), details of supplemental oxygen received (standard and/or high flow), and details of any mechanical ventilation will be collected.

Note: Principal Investigator or a medically qualified Sub Investigator may discharge a patient if (s)he considers the patient to be clinically fit and eligible (per applicable National Regulations/ Hospital practice) for discharge. After discharge, a telephonic follow up will be performed on Day 10, Day 14, Day 21 and Day 28 (as applicable for the individual patient, depending on the actual day of his/her discharge).

6.1.5 Telephonic follow up on Day 10, Day 14, Day 21 and Day 28, as applicable for the individual patient

For patients who are discharged before Day 28, a telephonic follow up assessment will be performed on Day 10 (applicable only for patients who are discharged earlier than Day 10 and if patients are unable to visit the site for EOT on Day 10), Day 14, Day 21 and Day 28 **as applicable**

Study code: NV-05-983-2020
 Protocol No.: CVD-04-CD-001
 Sponsor name: [name], Limited
 Clinical Study Protocol

for the individual patient (window period for telephonic follow up is +2 days from scheduled day of follow up). The patients will be followed-up for:

- a. safety reasons (eg. follow-up on AEs),
- b. to report a clinical relapse of COVID-19 (the patient will be asked if they have had any of the symptoms of COVID 19 after they were discharged).

An additional visit to the hospital (for further assessment) may be scheduled for such patients, if required. Details of concomitant medication will be recorded. The assessments to be performed at an unscheduled visit are mentioned in [Section 6.3.2.3](#) and [Table 2](#).

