3.1.3.2 Stage II

3.1.3.2.1 Efficacy Endpoints:

1. Percentage of patients reporting a clinical relapse of COVID-19 when assessed from day of discharge to 59 days after randomization (Day 60).

Note: 'Clinical relapse' is defined as either the reappearance or worsening of severity (over the assessment on the day of discharge) of one or more of the above-mentioned COVID-19 associated symptoms, or the appearance of any of these symptoms (due to COVID-19 infection) for the first time after discharge.

2. Proportion of patients
 - a. With disease worsening and requires:
 - Admission to ICU
 - High flow nasal oxygen
 - Non-invasive mechanical ventilation
 - Invasive mechanical ventilation

AND

- b. Dying

until Day 60 (regardless of whether patients are discharged from hospital before Day 28 or not)

3.1.3.2.2 Safety Endpoints:

1. Number (and percentage) of patients reporting treatment emergent adverse events (TEAEs) (by MedDRA system organ class and preferred term)

Secondary endpoints may be modified, or additional secondary endpoints may be defined in the SAP.

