6.3.2.2 Telephonic follow up on Day 60 (+2 days)

- Treatment emergent AEs
- COVID-19 associated symptom enquiry for assessment of clinical relapse
- Concomitant medication

6.3.2.3 Unscheduled Visit: If further assessment is found to be necessary on Telephonic Follow up

- COVID-19 associated symptom severity assessment
- Collection of a respiratory tract sample (nasopharyngeal swab or oropharyngeal swab or nasal aspirate or tracheobronchial aspirate or bronchial lavage) for detection (qualitative) of SARS-CoV-2 (by RT-PCR assay)*
- Partial physical examination*
- Vital signs*
- Chest X-ray*
- 12 Lead ECG*
- Clinical Laboratory assessments (haematology, serum biochemistry and urinalysis)*
- Treatment emergent AEs
- Concomitant medication*
- ICU admission status, supplemental oxygen (standard and/or high flow) and mechanical ventilation details*

** Assessments maybe performed at Investigator's discretion for individual patients for evaluation of patient safety or follow up of adverse events.*

Study code: NV-05-983-2020
 Protocol No.: CVD-04-CD-001
 Sponsor name: [name], Limited
 Clinical Study Protocol

Table 2: Study Assessment Schedule

Assessments	STAGE I – Main Study ¹											Data base Lock	Stage II – Extended Follow Up ²		Unsche duled Visit	
	Scree ning ³	Randomization (Baseline) ⁴					EOT ⁵			End of Study	42		60			
Day	-3 to -1 (72 hrs)	1 (Pre- dose)	1 (Post- dose)	On all days until discha rge	On all days until Day 10	4	5	7	10	14	21	28 or dischar ge				
Window Period	N/A	0	0	N/A	N/A	0	0	0	0/+2	0/+2	0/+2	0/+2		+2	+2	

¹ Stage I of the study includes a treatment period of 10 consecutive days and a study data collection period until Day 28. The treatment period may be shortened if it is necessary to discontinue administration of the study drug due to AEs or other circumstances. Principal Investigator or a medically qualified Sub Investigator may discharge a patient, if (s)he considers the patient to be clinically fit and eligible (per applicable National Regulations/ Hospital practice) for discharge. After discharge, telephonic follow up will be performed on Days 10, 14, 21 and 28 (as applicable for the individual patient, depending on actual day of discharge). For patients who remain admitted in the hospital until Study Day 28, the End of Study assessments will be performed on Day 28. A window period of 2 days will be allowed for the telephonic follow ups.

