¹⁶ Vital signs will be assessed on all days (Day 1 to Day 28 or until discharge, whichever is earlier). Includes SpO₂, body temperature (axillary), systolic BP, diastolic BP, pulse rate, and respiratory rate. Vital signs will be measured at pre-dose only on Day 1 and at least twice, morning and afternoon, daily from Day 2 to Day 28 or until discharge, whichever is earlier.

¹⁷ Includes general appearance, skin, head, neck, ENT, heart, lungs, abdomen, extremities, neurological, musculoskeletal, and lymph nodes

¹⁸ Includes general appearance, ENT, heart, lungs and lymph nodes.

¹⁹ The patients will be discharged when the Principal Investigator or a medically qualified Sub Investigator judges that the patient is fit for discharge. If the patient is discharged before Day 10, the remaining treatment course will be continued at home.

Study code: NV-05-983-2020
 Protocol No.: CVD-04-CD-001
 Sponsor name: [name], Limited
 Clinical Study Protocol

Assessments	STAGE I – Main Study ¹											Data base Lock	Stage II – Extended Follow Up ²		Unsche duled Visit	
	Scree ning ³	Randomization (Baseline) ⁴						EOT ⁵			End of Study		42	60		
Day	-3 to -1 (72 hrs)	1 (Pre- dose)	1 (Post- dose)	On all days until discha rge	On all days until Day 10	4	5	7	10	14	21	28 or dischar ge				
Concomitant Medications		•	•	•						•	•	•		•	•	•
Pre-treatment Adverse Events	•	•														
Treatment Emergent Adverse events			•	•						•	•	•		•	•	• ²⁰
ICU admission status, supplemental oxygen and mechanical ventilation details ²¹			•	•												•
Clinical relapse ²²									•	•	•	•		•	•	

²⁰ Treatment Emergent Adverse Events will be assessed and recorded in case of patients in whom the follow up (unscheduled) visit was necessitated for follow up of an adverse event/reporting of a new Treatment Emergent Adverse Event after discharge.

²¹ Will be evaluated on all days during the study period (until Day 28 or discharge, whichever is earlier) and also may be evaluated when patient returns for additional visit

²² Patients will be asked if they experience any COVID-19 symptoms after discharge.

Study code: NV-05-983-2020
Protocol No.: CVD-04-CD-001
Sponsor name: [name], Limited
Clinical Study Protocol

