9 SAFETY ASSESSMENTS

9.1 Adverse Events

All clinical AEs occurring after the patient signs the Informed Consent Form and up to Day 60 or study discontinuation, whichever is earlier whether observed by the Investigator or reported by the patient, will be recorded on the AE electronic case report form (eCRF) page. All SAEs are to be reported according to the procedures in [Section 9.2](#) SAE Reporting-Procedure for Investigators. Pre-planned procedure or hospitalization for pre-existing conditions which do not worsen in severity should not be reported as SAEs (see [Section 9.1.1](#) for Definitions).

At each visit, the Investigator will determine whether any AEs have occurred by evaluating the patient. Adverse events may be directly observed, reported spontaneously by the patient or by questioning the patient at each study visit. Patients should be questioned in a general way, without asking about the occurrence of any specific symptoms. All laboratory values must be appraised by the Investigator as to clinical significance. All post-baseline abnormal laboratory values considered clinically significant by the Investigator must be recorded in the AE page of the eCRF.

Investigator should follow patients with AEs until the event has resolved or the condition has stabilized. In case of unresolved AEs including significant abnormal laboratory values at the end of study assessment, these events will be followed up until resolution or until they become clinically not relevant.

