- The laboratory abnormality is not otherwise refuted by a repeat test to confirm the abnormality
- The abnormality suggests a disease and/or organ toxicity, then the underlying condition should be captured as an AE.
- The abnormality is of a degree that requires active management; e.g. change of dose, discontinuation of the drug, more frequent follow-up assessments, further diagnostic investigation, etc.

Study code: NV-05-983-2020
 Protocol No.: CVD-04-CD-001
 Sponsor name: [name], Limited
 Clinical Study Protocol

Lab abnormalities found during the screening assessments will not be considered as AE but will be used by the Investigator in determining eligibility of the individual patient for study participation and included as part of the medical history.

Hospitalization, Prolonged Hospitalization or Surgery

Any AE that results in hospitalization or prolonged hospitalization should be documented and reported as a SAE. Any condition responsible for surgery should be documented as an AE if the condition meets the criteria for an AE.

Neither the condition, hospitalization, prolonged hospitalization, nor surgery are reported as an AE in the following circumstances:

- a) Hospitalization or prolonged hospitalization for diagnostic or elective surgical procedures for a pre-existing condition. Surgery should not be reported as an outcome of an AE if the purpose of the surgery was elective or diagnostic and the outcome was uneventful.
- b) Hospitalization or prolonged hospitalization required to allow efficacy measurement for the study.
- c) Hospitalization or prolonged hospitalization for therapy of the target disease of the study, unless it is a worsening or increase in frequency of hospital admissions as judged by the clinical Investigator.

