10.6 Efficacy Analysis

10.6.1 Primary Efficacy endpoint

Primary Efficacy endpoint will be as follows:

1. Time to resolution of hypoxia

The primary efficacy endpoint is “Time to resolution of hypoxia (Time frame: Up to 28 days)”

This endpoint will be considered to have been met when the patient has attained a score of 4 or lower on the 10-point ordinal scale of clinical status and either of a) or b), (as applicable) and c) is met:

- a) Score is ≤ 4 on consecutive assessments over the next 5 days, if patient continues to remain in hospital (i.e., has not been discharged).

OR

Statistical Analysis Plan
Sponsor: [name], Inc

Study Number: NV-05-983-2020

Version: 2.0 Date: 06JAN2021

- b) Patient was discharged before five consecutive assessments (after reaching a score of 4)

AND

- c) The patient has survived and has not been re-admitted to hospital for COVID-19 management through Day 28.

*Note: Part c) is applicable to patients in both a) and b).
 i.e. Time to resolution of Hypoxia = either "a and c" OR "b and c" is met.*

Time to resolution of hypoxia will be compared between the treatment groups using the Cox proportional hazard model with age, gender, and baseline score on the 10-point ordinal scale of clinical status as covariates. The hazard ratio and its corresponding two-sided 95% confidence interval (CI) and two-sided p -value at 5% level of significance will be obtained from the above Cox proportional hazard model.

As the patients were in the hospital until discharge, missing data in the daily WHO clinical status score were few. To facilitate the definition of the durable response, a very limited and conservative imputation will be implemented to impute a missing clinical status score if adjacent to a valid score on both sides, the imputed score will be the higher (worse) of the two, as discussed in Section 9.5.1.

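### No scheduled post-discharge contact collects readmission, vital status or escalation of care as a required item, although part (c) of the primary endpoint and Stage II endpoint 2 need them

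*Protocol*

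**What the plan says.** **What the endpoints need.** SAP 10.6.1 and Protocol 3.1.3.1.1 make a resolution of hypoxia count only if condition (c) holds: "The patient has survived and has not been re-admitted to hospital for COVID-19 management through Day 28". SAP Appendix I applies the same condition at the interim analysis. Stage II endpoint 2 (Protocol 3.1.3.2.1) counts ICU admission, high-flow oxygen, non-invasive or invasive ventilation, and death "until Day 60 (regardless of whether patients are discharged from hospital before Day 28 or not".

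**What is collected after discharge.** Protocol 6.1.5 gives the calls two purposes: following up adverse events and detecting relapse, for which "the patient will be asked if they have had any of the symptoms of COVID 19 after they were discharged". Sections 6.3.1.6, 6.3.2.1 and 6.3.2.2 itemise the calls identically: treatment-emergent AEs, concomitant medication, and "COVID-19 associated symptom enquiry for assessment of clinical relapse". In Table 2 the row for ICU, oxygen and ventilation is marked for in-hospital days and the unscheduled visit, not for Days 42 or 60. Footnote 21 limits it to Day 28 or discharge, "and also may be evaluated when patient returns for additional visit".

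**Day 10.** Patients discharged before Day 10 have a site or home contact (6.3.1.4). The on-site version grades symptoms, but its ICU, oxygen and ventilation item is at the investigator's discretion. The home version adds a blood sample to the same three call items.

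**Relapse.** One limb of the definition is "worsening of severity (over the assessment on the day of discharge"; the others are reappearance and first appearance.

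**The concern.** Part (c) helps to define the primary event. A patient who reaches a score of 4 or lower and goes home is a success only if no death or COVID-19 readmission follows by Day 28. If nobody is required to ask, a readmission to another hospital can stay unknown and the resolution stands. The same data drive the interim decisions on efficacy, futility and sample size. In Stage II, a post-discharge escalation that is not reported is counted as no worsening.

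Other data do not fill the gap. The 10-point scale stops at discharge (Table 2, footnote 13), and secondary endpoints 12 to 15 stop at Day 28 or discharge, whichever is earlier. The guidance reproduced as Protocol Appendix I asks sponsors to aim for vital status on every subject and to deal with relapse in the endpoint definition.

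**Working it through.** **1. The plan's own event count.** Inputs (Protocol 11.10, SAP 9.6): hazard ratio 1.25, two-sided alpha 0.05, power 80%, 1:1 allocation. By Schoenfeld's formula, events = 4(z₀.₉₇₅ + z₀.₈₀)² / (ln 1.25)² = 4(1.960 + 0.842)² / 0.2231² ≈ 631, as stated. With 371 per arm and event probabilities 0.9 and 0.8: 371 × 0.9 + 371 × 0.8 = 630.7.

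**2. Need against collection, after discharge.**

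| Item | Needed for | Required at a scheduled contact? | Other route |
|---|---|---|---|
| COVID-19 readmission to Day 28 | Part (c) | No | SAE report, with an exception; discretionary visit |
| Vital status to Days 28 and 60 | Part (c); Stage II endpoint 2 | No | SAE report; AE outcome; discontinuation reason |
| ICU, high-flow oxygen, ventilation to Day 60 | Stage II endpoint 2 | No | SAE report if judged a deterioration; discretionary item at a visit |
| Symptom grade | Worsening limb of relapse | Only at the Day 10 on-site visit | Unscheduled visit, if held |

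A patient who answers a call is plainly alive, so vital status is open only for patients not reached.

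**3. How far the AE/SAE route goes.** Reporting runs to Day 60, and death and inpatient hospitalization are seriousness criteria. But Protocol 9.1.1.2 lists among the circumstances not reported as an AE: "Hospitalization or prolonged hospitalization for therapy of the target disease of the study, unless it is a worsening or increase in frequency of hospital admissions"; the investigator decides which applies. Giving supplemental oxygen is not in itself an SAE without significant deterioration. On AE enquiry, Protocol 9.1 says: "Patients should be questioned in a general way, without asking about the occurrence of any specific symptoms".

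**4. What the SAP does.** SAP 10.6.1 restates part (c) and SAP 10.6.2 tabulates Stage II endpoint 2; neither names a data source. The SAP 9.3 derivation of time to resolution mentions neither survival nor readmission. The censoring rules sort patients already classed as unresolved. They do not say how to class a discharged patient whose readmission status is unknown.

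**5. Scale (assumption).** The documents give no post-discharge readmission or death rate. If 1% of the 631 counted resolutions were in truth voided by part (c), 631 × 0.01 ≈ 6 would be false; at 4%, 631 × 0.04 ≈ 25. Removing false events costs little power. With power = Φ(√events × ln 1.25 / 2 − 1.960):
- 631 events: 80.0%
- 1% removed (625 events): 79.6%
- 3% removed (612 events): 78.8%
- 5% removed (599 events): 78.0%

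The issue is misclassification, not power.

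**6. Direction.** Suppose a share s of true Stage II events is detected in both arms, with no false positives. The risk ratio is s·p₁ / s·p₀ = p₁/p₀, unchanged; only the difference, s(p₁ − p₀), shrinks. For the primary endpoint, the direction depends on whether treatment changes readmission or how it is reported. The documents give neither.

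**The case against.** A reader might infer that nothing measures part (c) or Stage II endpoint 2 after discharge. The documents do not support that:

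- Every call collects adverse events, and SAE reporting runs to Day 60.
- The AE record has a fatal outcome category (9.1.1.6) and a category for hospitalization as the action taken (9.1.1.7).
- Death is a study-discontinuation reason (3.1.6.1.1).
- Respiratory failure needing invasive ventilation is given as an example of an SAE (9.1.1.2).
- Patients are told to report symptoms and side effects until Day 60 (5.1.8).
- Many COVID-19 readmissions would count as a worsening and escape the target-disease exception. The rule on general AE questioning bars prompting for specific symptoms, not asking about hospital stays.
- For Stage II endpoint 2, in-hospital escalation is recorded daily to Day 28 or discharge, so only the post-discharge part is exposed.

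Nor does it follow that a persisting symptom can never be told from a relapse. Severity is recorded at discharge, so reappearance and first appearance need only presence at the call, provided it notes which symptom. Only the worsening limb needs a later grade, and one is taken if an unscheduled visit is held.

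Finally, the SAP cites eCRF Final 3.0, which was not available and may already hold such fields. It is dated 26 November 2020, before protocol 5.0 of 6 January 2021, but that does not show the fields are absent.

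What stands after all this: capture rests on reporting and judgement rather than a required question, the exception applies to the very admissions part (c) is about, and the visits are discretionary.

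**Conclusion.** The point holds in a limited form. As the protocol is written, a condition that defines the primary event, and the post-discharge part of Stage II endpoint 2, are not ascertained systematically. The calls also lack the grade that one of the three relapse limbs needs.

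The size is unknown. The range of 6 to 25 events in 631 rests on an assumed 1% to 4% and is an illustration, not an estimate. A reader might also infer dilution toward no difference in both comparisons. The documents do not establish that: equal under-detection leaves the Stage II risk ratio intact, and the effect on the primary hazard ratio needs information the plan does not give. The conclusion is subject to what the eCRF holds. It still merits action, because it touches the primary endpoint and the remedy is cheap.

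**What to change.** **Protocol and eCRF.** At every scheduled post-discharge contact (Days 10, 14, 21, 28, 42 and 60, including the Day 10 site or home contact), require:
- vital status, with date of death if applicable;
- any readmission since the last contact, with dates and whether it was for COVID-19;
- any ICU stay, oxygen, high-flow oxygen, non-invasive or invasive ventilation since the last contact, with dates;
- a 0 to 4 grade for each listed symptom.

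Dates matter because the two-day window lets the Day 28 call fall after Day 28. Patients already past Day 28 can be asked retrospectively at the Day 42 or Day 60 call.

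**SAP.** Derive part (c), Stage II endpoint 2 and relapse from these fields, bring the SAP 9.3 definition into line with part (c), and state how patients who cannot be reached are classified.

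**Cost.** Slightly longer calls, an eCRF update if the fields are not already there, and possibly a few fewer primary events. No new visit is needed.
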